2.6.3 Phase II Study of CPX-351: CLTR0308-205

This study compared CPX-351 (100u/m²; Day 1, 3, 5) with salvage therapy in first relapse AML patients. This trial planned to accrue 120 patients with a 2:1 randomization. Investigator choice of control salvage regimen was expected to be between (1) high dose cytarabine with or without daunorubicin, (2) 7+3 or (3) mitoxantrone, etoposide and cytarabine. The allowance of investigator's choice reflects the fact that no single salvage therapy is superior and the necessity of individualizing treatment. Responding patients were expected to receive allogeneic stem cell transplant for consolidation if donors were available.

The European Prognostic Index was used to stratify patients. For this trial, the primary endpoint was survival at one year, which for the control arm was expected to be $\leq 30\%$ based on previous clinical trials and the literature. Secondary endpoints were CR+CRi rate, remission duration, event-free survival and 30/60/90 day mortality. The 1 year survival rate was selected as the primary endpoint rather than response rate because of the substantial variability of the CR rate for different salvage regimens reported in the literature. Accrual was completed in November 2010 with 81 patients randomized to CPX-351 and 45 randomized to salvage therapy.

Patient demographics were well balanced between the two arms for durations of first complete remission, cytogenetics, and age. There was a slight imbalance in history of prior stem cell transplants with more patients in the CPX-351 arm having a history of transplant. Study stratification was successful with approximately 2/3's of patients in both study arms in the unfavorable EPI risk group.

205 Study Patient Demographics

	EPI Points	CPX-351 n=81		Control n=44	
		n (%)	n (%)	n (%)	n (%)
Risk Group	Favorable	1-6	9 (11.1)	6 (13.6)	
	Intermediate	7-9	16 (19.8)	9 (20.5)	

	Unfavorable	10-14	56 (69.1)	29 (65.9)
	> 18	0	11 (13.6)	8 (18.2)
Relapse-Free Interval from CR1 (months)	7-18	3	43 (53.1)	20 (45.5)
	≤ 6	5	27 (33.3)	16 (36.4)
	Inv(16) or t(16;16)	0	7 (8.6)	4 (9.1)
Cytogenetics at Diagnosis	t(8;21)	3	2 (2.5)	1 (2.3)
	Other	5	72 (88.9)	39 (88.6)
	≤ 35	0	10 (12.3)	4 (9.1)
Age at First Relapse (years)	36 - 45	1	14 (17.3)	7 (15.9)
	> 45	2	57 (70.4)	33 (75.0)
HSCT before Relapse	No	0	59 (72.8)	37 (84.1)
	Yes	2	22 (27.2)	7 (15.9)

[figure not shown]
Consistent with results observed in Study 204, this study in patients with first relapse AML also demonstrated higher rates of treatment induced hypoplasia/aplasia and response with improvements in median EFS and OS.

Aplasia, Response, and Early Mortality Results

	Overall (n=125)		Unfavorable EPI Risk (n=85)	
	CPX-351 (n=81)	Salvage (n=44)	CPX-351 (n=56)	Salvage (n=29)
Aplasia Rate	77.3%*	59.5%*	66.10%	44.80%
CR Rate	37.00%	31.80%	28.60%	20.70%
CRi Rate	12.40%	9.10%	10.70%	6.90%
Response Rate	49.40%	40.90%	39.30%	27.60%
60-Day Mortality	14.80%	15.90%	16.10%	24.10%
EFS (median)	4.0 months	1.4 months	2.0 months	1.2 months
OS (median)	8.5 months	6.3 months	6.6 months	4.2 months

The EFS and OS results did not demonstrate statistically significant improvements for the group as a whole, but significance was found for survival in the subset of relapsed patients with EPI Unfavorable disease. These results echo those found for the secondary AML population in Study 204, in that significant differences in patient outcomes were observed in patients with less sensitive AML because of a substantial fall off in efficacy for the control arm.

Overall Survival and Event-free survival in patients with EPI Unfavorable disease

A search for imbalances that could have biased study results in favor of CPX-351 was also performed and imbalances in post-induction bone marrow transplants were not found. The rate of post-induction HSCT was similar between the two study arms among patients with CR, CRI, and persistent AML, suggesting that transplants did not bias the study.

[figure not shown]
Safety data were consistent with those from Study 204. Patients with no history of prior stem cell transplant at study entry were in the majority (96/125, 76.8%) and were found to have slightly lower 60-day mortality (10.2% vs. 16.2%) and higher complete response rates (54.2% vs. 37.8%). Patients with prior stem cell transplants had poorer results after CPX-351 with somewhat higher 60-day mortality (27.3% vs. 14.3%) and lower response rate (35.4% vs. 57.1%). The prior stem cell transplant group was too small to reach definitive conclusions but it is possible that patient groups with extensive prior chemotherapy may be at higher risk following CPX-351 treatment.

Overall, Study 205 confirmed and extended observations first made in Study 204. CPX-351 is highly active with improved clearance of leukemia and higher response rate, even in patients with prior exposure to cytarabine and anthracycline. CPX-351 was also shown to be safe with improved 60-day mortality in the majority of patients with no prior history of HSCT. These results suggest that CPX-351 will be an excellent candidate to test in newly diagnosed AML patients with high risk of treatment mortality.

2.7 Copper Background

Copper is an essential element that is a component of a number of metalloenzymes acting as oxidases (e.g. diamine oxidase, monoamine oxidase, cytochrome c oxidase). The median absorption of copper from food (by an American adult) is 1.0 to 1.6 mg/day. The tolerable Upper Intake Level for adults is 10 mg/day. At a dose of CPX-351 of 100 u/m², a patient with a BSA of 2.0 m² would receive a maximum of 36 mg of elemental copper per dose. In the animal toxicology investigations for CPX-351, elevated copper levels were seen following dosing with levels generally returning to baseline 1 to 2 weeks after the last dose (see Figure 5). No toxicity seen in animal studies was attributable to copper.

The data from the clinical studies are consistent with the preclinical findings. Since CPX-351 contains copper (0.18 mg copper per unit, in the form of copper gluconate), serum total copper levels were monitored in the Phase 1 clinical study (Study CLTR0305-101). Figure 5 shows this data for cohort 9 (n=20, dose 101 units/m²) graphically:

Figure 5: Median and Mean Serum Copper in Cohort 9 after the First Induction

As Figure 5 shows, both the median and mean copper levels in patients receiving 3 doses of CPX-351 at 101 units/m² was very high on day 7 (2 days after the last dose) but returned to normal levels in most patients by day 14. All patients had serum copper levels in the normal range by day 42 after the first induction. In summary, no safety problems are expected due to systemic copper exposure from CPX-351.

In this trial, serum copper levels will be monitored and elevated levels are assumed to be due to copper gluconate encapsulated within the CPX-351 liposome rather than free circulating copper. Clinical observation from a single patient treated with the identical copper-containing liposome encapsulating a different chemotherapy doublet (CPX-1, floxuridine and irinotecan) demonstrated sustained elevations of copper in a patient during a period of biliary obstruction, with return to baseline levels after stenting relieved the obstruction. This anecdote suggests that copper elimination after CPX-351 is likely via biliary excretion and elimination in the feces. Preclinical studies completed by Celator (acquired by Jazz Pharmaceuticals) demonstrated that virtually all of the copper administered in the form of CPX-351 is excreted via the feces within approximately 2 weeks of administration. It is expected that eligible patients with unobstructed biliary systems should be able to eliminate the copper administered within a few weeks. Serum copper levels will be monitored until they return to baseline levels ($\pm 20\%$) and patients will be monitored for hepatic dysfunction, a common manifestation of copper-related toxicity.

3.0 Study Objectives and Rationale

3.1 Primary Objectives

The primary objective of this study is to assess preliminary efficacy (as determined by the rate of CR or CRI) of two or three dose levels of CPX-351 in patients with newly diagnosed AML at high risk for induction mortality, defined as 30-50% predicted risk of death by Day 60, and to select the most promising dose level for further efficacy testing. Estimation of risk for induction mortality at patient screening will be based on factors associated with lower likelihood of AML response with or without factors that reduce tolerance to treatment-associated adverse events.

3.2 Secondary Objectives

To confirm the rate of dose limiting toxicities, including induction mortality (at day 60) for two different sub-MTD dose levels (50 and 75 U/m²). If safety results suggest feasibility to test the MTD dose level of CPX-351 (100 U/m²) in patients believed to be at high risk for induction mortality, the rate of dose limiting toxicities and induction mortality will be tested in this group as well.

3.3 Exploratory Objectives

To investigate the effect of CPX-351 on immune response, as determined by the effect on recovery of functional pathogen-specific and leukemia-specific immune responses and the recovery and function of NK cells.

To investigate the role of Troponin-T as an early marker for CPX-351-induced cardiotoxicity.

To investigate ex vivo the cytotoxicity of combination of Pim kinase inhibitor(s) and CPX-351 on circulating leukemia cells.

3.4 Study Rationale

The Phase I study identified the MTD in fit relapsed and refractory adult leukemia patients and confirmed that the intended 5:1 molar ratio was maintained for cytarabine:daunorubicin across multiple dose levels with markedly prolonged plasma half life of cytarabine and daunorubicin. At the MTD, CPX-351 was detectable in plasma at least 7 days after the last dose (Study Day 12). A substantial number of responses were observed among late stage patients already previously treated with cytarabine and daunorubicin.

The randomized Phase II results with CPX-351 suggest that CPX-351 is likely better tolerated than conventional cytarabine and daunorubicin-based chemotherapy with reduced 60-day mortality (4.6%) observed among newly diagnosed patients. Moreover, preclinical observations that CPX-351 concentrates in bone marrow with evidence for relatively selective internalization of liposomes within the cytoplasm of leukemia cells

suggests that CPX-351 action will be potent and that non-hematopoietic toxicities will be modest. Clinical observations from the Phase I study of complete response occurring at dose levels as low as one third to one half the MTD (32 to 43 units/m²), strongly suggest that 25% and 50% dose reductions to 75 and 50 units/m² will still be effective and should be better tolerated. By using reduced dose CPX-351 as induction therapy it may be possible to improve the outcome of patients with AML considered at high risk for 60-day mortality, patients not ordinarily offered induction therapy for AML at all.

Data from the Phase I and both Phase II studies also demonstrated a relatively shallow dose/toxicity curve, with relatively little increase in non-hematopoietic toxicities with increasing doses up to the MTD. If sub-MTD dose levels of CPX-351 are well tolerated in patients at higher risk of early mortality, it may be possible to evaluate treatment at the MTD for patients at high risk for induction mortality. To the extent that higher dose levels maximize treatment efficacy, demonstration of treatment safety and feasibility at the MTD may permit treatment with the most efficacious dose level in patients at high risk for induction mortality.

4.0 Study Design

One cycle equals 28 days.

This study is an open-label, two-arm or possibly 3-arm, phase II trial. CPX-351 is administered as approximately a 90-minute infusion on days 1, 3, and 5 with one study arm receiving 50 units/m² and the other receiving 75 units/m². Both the 50 and the 75 unit/m² dose levels are considered to have acceptable safety based on observations from a pair of randomized Phase II studies conducted in adult patients, where the observed 60-day mortality results in patients considered fit for intensive chemotherapy and with no prior history of stem cell transplant, was observed to be reduced compared to control.

Patients with newly diagnosed AML who are predicted to be at high risk (30-50%) for induction mortality (death by day 60) are eligible. Every patient entered must have at least one AML-related factor (adverse cytogenetics, secondary AML, MDR phenotype, etc.) that contributes to elevated risk of induction mortality. Patients may or may not have patient-related factors (poor performance status, co-morbidities, poor organ function, etc.) that also contribute to elevated risk of induction mortality. 30 patients will be randomized with a 1:1 ratio to the two dose arms with 15 patients per arm to assess for safety and efficacy. If safety is demonstrated for both of the sub-MTD dose levels, and escalation is deemed feasible above 75 units/m², a cohort of 15 patients will be studied at 100 units/m², the MTD dose level. The latter dose (i.e., 100 units/m²) was found safe and an additional 25 patients will be enrolled at this dose (for a total of 40 evaluable patients) to define efficacy at this standard dose.

At the end of the study a single dose level will be confirmed to have acceptable safety if the observed rate of dose limiting toxicity (DLT) is <5 DLT/15 patients.<33%). Dose limiting toxicity is defined as induction mortality (death occurring during the first 60 days from start of study therapy), grade 3 or 4 non-hematologic toxicity, or dose limiting

hematologic toxicity at least possibly related to the study drug occurring during the first 60 days from the start of study therapy (i.e., during the first cycle of therapy).

For non-hematologic toxicity the following are counted as dose limiting toxicities only under the conditions noted:

- Liver toxicity: Grade 4, related to the study drug, not resolving to grade 2 within 7 days.
- Decrease in ejection fraction: Grade ≥ 3 (nadir LVEF $<40-20\%$), related to study drug
- Creatinine elevation: Grade ≥ 3 , related to study drug.
- Any other adverse event of Grade ≥ 3 , related to study drug that in the opinion of the PI is inconsistent with the expected adverse events with standard chemotherapy.

Dose limiting hematologic toxicity is defined by bone marrow and peripheral blood examination at Day ≥ 56 showing:

- Absence of recurrent or persistent leukemia AND
- Persistently hypocellular marrow ($<20\%$ cellularity) AND
- Peripheral blood:
 - ANC < 500 and/or
 - Platelet count $< 10,000$

If more than one dose level is considered acceptably safe, the decision about which one to use for future clinical study will be based on efficacy. Efficacy success for an individual patient is defined as achievement of CR or CRI. Observation of ≤ 3 CR or CRI among 15 patients ($\leq 20\%$) defines a non-efficacious study arm. In situations where both study arms are considered equally safe, the study arm with the higher rate of response will be recommended for future study, provided it equals or exceeds 20%.

When the dose recommended for future study is defined, 10 additional newly diagnosed patients will be treated at that dose level (not to exceed a total of 25 patients at that dose level) to obtain additional evidence of safety and efficacy among previously untreated patients with high risk of induction mortality.

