10.0 Statistical Considerations(16, 17)

General Description:

This is a Phase II study of CPX-351 Liposome Injection in newly diagnosed AML patients with high risk of induction mortality. Two dose levels (50 units/m² and 75 units/m²) of CPX-351 will be studied initially. The primary objective is to evaluate treatment response. The efficacy outcome is CR or CRi within two induction cycles. A maximum of 30 patients will be equally randomized to the two dose levels. A Bayesian method by Thall et al (1995)

will be used for futility and toxicity monitoring. After 15 patients have been accrued to each dose level, an assessment of overall safety/dose limiting toxicities and efficacy will be made and one dose level will be chosen for further study. OR if both dose levels are safe and further dose escalation seems possible, one additional cohort with a dose of 100 units/m² will be open. A maximum of 15 patients will be enrolled in this arm and the same toxicity and futility monitor rules will be applied. After 2 or 3 dose levels have been studied, one dose levels will be chosen for further study. An expansion cohort of 10 patients will be treated at the dose level with a favorable response and/or toxicity profile for further evaluation for safety and efficacy. Consequently, the preferred dose level has 25 patients evaluable.

Additional 25 patients will be added to the arm with the dose of 100 units/m², the sample size for this arm will be up to 40, and the maximum number of patients for all three arms will be up to 80.

Multc Lean software version 2.1 developed in the Department of Biostatistics MDACC was used for the study design.

The study will monitor futility and toxicity, and the monitoring rules will be applied to each dose separately. If study in one of the two doses is stopped early due to futility or excessive toxicity, all the future patients will be enrolled in the open dose arm (i.e., without randomization). In the case the lower dose (50 units/m²) has been shown to be too toxic at an interim look (thus stop further patient enrollment) the higher dose (75 units/m²) will also stop accrual.

Futility monitoring:

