# Responses (inclusive)	
5	0
10	0-1
15	Always stop with this many patients

Toxicity monitoring

In addition, toxicity will be monitored closely. Denote the probability of toxicity by T_E , where toxicity is defined as DLTs. We assume toxicity rate beta (0.66, 1.34) for the experimental treatment in this study. Our safety monitoring rule is described as follows: $\Pr(T_E > 0.33 | \text{data}) > 0.85$. That is, we will stop the enrollment in one dose if, at any time during the study, we determine that there is more than 85% chance that the DLT rate is more than 33% in that dose. Stopping boundaries corresponding to this stopping rule is listed in table 8. For example, the enrollment in one dose will be stopped if the first 4 of the first 5 patients experienced toxicity in that dose.

Table 8: Stopping boundaries for toxicity monitoring for the initial cohort of each dose (n=15)

# Patients (in complete cohorts of 5) (inclusive)	Stop the enrollment in dose level if there are this many DLTs total in that dose level:

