The arm with a favorable toxicity profile and/or a favorable might be chosen for further evaluation by expanding a cohort of 10 additional patients in that arm. We will use the same criteria (e.g. expansion will be stopped if $\Pr(T_E > 0.33 | \text{data}) > 0.85$) to monitor toxicity for the expansion cohort by using a total sample size of 25 for the winner arm. The stop boundaries are summarized in the following table. If 10 or more patients out of the 1st 20 patients experienced DLT, the trial will be stopped and no expansion cohort will be evaluated. If 10 or more patients out of 20 patients experienced DLT (by adding 5 more patients to the 15 patients in that arm), the expansion will be stopped.

Table 11. Toxicity monitoring for the expanded cohort at a dose of 75 units/m²

# Patients (in complete cohorts of 5) (inclusive)	Stop the arm with expansion cohort if there are this many dose limiting toxicities total:

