	# Toxicities (inclusive)
5	4-5
10	6-10
15	8-15
20	10-20
25	Always stop with this many patients

Expansion of arm with the dose of 100 units/m²

Up to additional 25 patients will be enrolled in this arm, thus total sample size for this arm is up to 40. Assuming that the success rate is binomially distributed, 40 patients will have has 99% power to detect a difference of 5% vs. 30% in success rate at a one-sided type I error rate of 0.05 using an exact test.

Similar futility and toxicity monitoring rules listed above will also be applied for the expansion of arm with 100 units/m². That is, the trial will be stopped early if

$$\Pr(\theta_E < 0.25 + \theta_S | \text{data}) > 0.98 \text{ for futility}$$

or

$$\Pr(T_E > 0.33 | \text{data}) > 0.95 \text{ for toxicity}$$

where θ_E represents the response rate for experimental drug in this study and θ_S represents the response rate for the standard practice (null hypothesis). T_E represents DLT rate. For trial simulation, we use the same assumption for prior distributions listed above for each parameter. That is, θ_S has a prior distribution of beta (10, 190), θ_E has a non-informative flat prior beta(0.1, 1.9), and T_E has a prior distribution of beta (0.66, 1.34).

Table 12 and 13 present the corresponding stopping boundary and operating characteristics (OCs).

Table 12: Stopping boundaries for futility and toxicity of the expansion cohort with the dose of 100 units/m²

N patients evaluated	Stop for toxicity if >= this number of patients experience DLT	Stop for futility if <= this number of patients achieve CR/Ci
5	4-5	0
10	7-10	0
15	9-15	0-1
20	11-20	0-2
25	13-25	0-3
30	15-30	0-4
35	17-35	0-5
40	19-40	0-6

Table 13: OCs of the expansion cohort with the dose of 100 units/m²

True CR+CRi Rate	True DLT Rate	Early Stopping Probabilities	Average sample size treated
0.05	0.1	0.9965	8.16
0.05	0.2	0.9965	8.14
0.05	0.33	0.9969	7.99
0.05	0.5	0.999	7.26
0.1	0.1	0.9294	13.16
0.1	0.2	0.930	13.10
0.1	0.33	0.9372	12.63
0.1	0.5	0.9803	10.19
0.2	0.1	0.5119	25.54
0.2	0.2	0.5156	25.39
0.2	0.33	0.5654	24.00

0.2	0.5	0.8637	16.36
0.3	0.1	0.2029	33.50
0.3	0.2	0.209	33.30
0.3	0.33	0.2903	31.31
0.3	0.5	0.7774	20.23
0.4	0.1	0.0817	37.19
0.4	0.2	0.0887	36.96
0.4	0.33	0.1824	34.70
0.4	0.5	0.7436	22.12
0.4	0.6	0.9612	14.02

Statistical methods:

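### The Section 4.0 safety criterion (fewer than 5 DLTs in 15, under 33%) is not carried to the 25- and 40-patient arms or tied to the looser Section 10 toxicity boundaries

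*Combined protocol and SAP*

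**What the plan says.** Section 4.0 sets the acceptance rule. It opens "At the end of the study a single dose level will be confirmed to have acceptable safety if the observed rate" and gives the limit as "the observed rate of dose limiting toxicity (DLT) is <5 DLT/15 patients.<33"%, that is, below 5 DLTs in 15, also written as below 33%. Death within 60 days of starting therapy is itself a DLT. The section then chooses among doses judged acceptably safe on efficacy, and adds 10 patients once the recommended dose is defined. It also reports that 100 units/m² was found safe and adds 25 patients there, for 40 in all.

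Section 10.0 monitors DLTs with a Bayesian rule. The prior is given as "We assume toxicity rate beta (0.66, 1.34) for the experimental treatment in this study", and enrolment in a dose stops if "there is more than 85% chance that the DLT rate is more than 33% in that dose". Table 8 turns this into counts for the initial cohorts: 4 of 5 and 6 of 10, with no toxicity count at 15. For the first 15 patients at 100 units/m², "the same toxicity and futility monitor rules will be applied".

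The 10-patient expansion keeps the 0.85 cutoff "to monitor toxicity for the expansion cohort by using a total sample size of 25 for the winner arm". The count column of Table 11 is headed "Stop the arm with expansion cohort if there are this many dose limiting toxicities total" and lists 4/5, 6/10, 8/15 and 10/20. For the 40-patient arm the cutoff rises to 0.95. The column of Table 12 headed "Stop for toxicity if >= this number of patients experience DLT" runs 4/5, 7/10, 9/15, 11/20, 13/25, 15/30, 17/35 and 19/40.

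**The concern.** The acceptance rule and the stopping rule both refer to a 33% DLT rate but draw the line in different places, and nothing links them. Three conflicts follow.

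1. **Expansion to 25.** The only counts attached to the expansion are those of Table 11 and the matching text. An arm with 5, 6 or 7 DLTs in 15 fails Section 4.0 and is not stopped. The safety judgement that comes before expansion (Section 4.0; Section 10.0, General Description and the text around Tables 10 and 11) carries no count.
2. **The 40-patient arm.** Enrolment can continue after the under-33% criterion has become unreachable, and a final count above it is not flagged.
3. **Count against rate.** Beyond 15 patients the two halves of the Section 4.0 criterion can give opposite answers for the same arm.

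At stake are the choice of expansion dose, the dose recommended for further study, and the continued enrolment of patients with a predicted 30–50% risk of death by day 60.

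**Working it through.** **Reproducing the plan's boundaries.** With x DLTs in n patients the posterior is Beta(0.66 + x, 1.34 + n − x). The boundary is the smallest x for which Pr(T_E > 0.33) exceeds the cutoff. At n = 15:

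| DLTs in 15 | Pr(T_E > 0.33) |
|---|---|
| 4 | 0.284 |
| 5 | 0.487 |
| 6 | 0.688 |
| 7 | 0.842 |
| 8 | 0.934 |
| 9 | 0.978 |

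A cutoff of 0.85 gives 8/15 and a cutoff of 0.95 gives 9/15, as printed. Every other toxicity boundary in Tables 8, 11 and 12 also reproduces. So do the operating characteristics checked. For response 0.3 and DLT rate 0.33, Table 9 prints 0.30 and 12.5 (recomputed 0.2998 and 12.48), and Table 13 prints 0.2903 and 31.31 (recomputed the same). The tables are correct for their own rule.

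**Both rules on one scale.** Section 4.0 accepts 4/15 and rejects 5/15. That corresponds to a posterior cutoff between 0.28 and 0.49, against 0.85 and 0.95 in Section 10.0.

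**What under 33% means for each arm size.** The limits are 4/15 (26.7%; 5/15 is 33.3%), 8/25 (32%; 9/25 is 36%) and 13/40 (32.5%; 14/40 is 35%).

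**Where the rules part.**
- Table 11 does not stop 5–7 of 15 (33–47%). It continues at 9/20, so an arm can finish at 9 + 5 = 14 of 25 (56%).
- Table 12 continues at 14/30 and at 14–16/35. Each already exceeds 13, so at most 13/40 is out of reach. At n = 40 it leaves 14–18 (35–45%) unflagged.
- An arm with 5 of its first 15 fails the count. If 2 of the next 10 have a DLT it ends at 7/25 (28%) and meets the rate.

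**How often.** Exact binomial enumeration, looks every 5 patients, printed toxicity boundaries only:

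| True DLT rate | Reaches 15 with 5–7 DLTs, not stopped | Completes 25 with ≥9 DLTs (Table 11) | Completes 40 with ≥14 DLTs (Table 12 from patient 1) |
|---|---|---|---|
| 0.20 | 0.152 | 0.039 | 0.018 |
| 0.30 | 0.401 | 0.235 | 0.245 |
| 0.33 | 0.458 | 0.306 | 0.354 |
| 0.40 | 0.510 | 0.398 | 0.486 |
| 0.50 | 0.382 | 0.284 | 0.260 |

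**With futility stopping** (Table 7 or the futility column of Table 12, response and DLT independent), at a DLT rate of 0.33: 46% becomes about 35% at a 30% response rate and about 25% at 20%. The 35% for the 40-patient arm becomes about 28% and 17%.

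**One assumption in the last column.** Section 10.0 puts the first 15 patients at 100 units/m² under the 0.85 rule (6/10), while Table 12 restarts at n = 5 with 7/10. Replacing 7 by 6 at n = 10 and keeping the rest of Table 12 moves 0.354 to 0.335.

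**The case against.** The strongest reply is that these are two different questions. Section 4.0 states a final acceptance criterion, and the Section 10.0 tables say when to stop enrolling. An interim boundary is commonly looser than the final bar, and no passage says that an arm which avoids a boundary is thereby safe. That stands. A reader might infer that Tables 8, 11 and 12 are wrong because they are looser, or that an arm at 5–7 of 15 is approved by Section 10.0. The documents support neither. Continuing after 5 DLTs in 10 also fits Section 4.3, which plans at least 15 patients per dose unless an early-stopping condition is met.

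Nor is expansion automatic. Table 8 ends every initial cohort at 15, Section 10.0 calls for a safety assessment there, and Section 4.0 can be read as placing acceptability before the extra 10 patients. But that assessment has no count and Section 4.0 dates its criterion to the end of the study. The Section 10.0 text lets a favourable toxicity profile and/or another favourable feature justify expansion. Its remaining bar, 10 of the first 20, cannot be evaluated when 15 have been treated. The gate exists but is undefined.

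A reader might also infer that escalation to 100 units/m² rested on the looser rule. The documents do not show this. Section 4.0 reports that dose as found safe without naming the rule used, so the escalation decision is largely past.

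Finally, it is tempting to conclude that accrual should end at the fifth DLT in 15. That would be a substantial redesign, and nothing shows it was intended. At a true DLT rate of 20%, 16% of arms would reach 5 of 15 (1 − 0.836), against 1% stopped by Table 8. At 30% the figures are 49% and 6%.

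**Conclusion.** The point holds as an unreconciled decision threshold, not as an error in the stopping tables. The documents do not say which count decides acceptability in a 25- or 40-patient arm, or whether it must be met before expansion. Table 12 permits enrolment after its own arm can no longer end under 33%.

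At a true DLT rate of 33%, the chance of reaching 15 patients unstopped with 5–7 DLTs is 46% on toxicity looks alone and about 35% with futility at a 30% response rate. The chance of completing 40 with 14 or more DLTs is 35% and about 28%. These figures assume looks at every fifth patient, independent response and toxicity, and Table 12 applied from the first patient.

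The true DLT rate is unknown. Rates near 33% are plausible because early death counts as a DLT and eligibility targets a 30–50% predicted risk, but treatment may lower that risk. At a rate of 20% the first figure is 15% and the second 2%, on toxicity looks alone. The claim that an arm at 5/15 has already failed is strict only if the count binds. If only the rate applies, the arm could still end at 8/25 or 13/40.

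**What to change.** Reconcile Section 4.0 with Tables 8, 11 and 12:
- State one final acceptability criterion as a count for n = 15, 25 and 40. If under 33% stands, the counts are at most 4, 8 and 13. If the posterior rule is meant, print its counts: below 8/15 and 11/25 at the 0.85 cutoff, and below 19/40 at 0.95.
- Say whether it must be met before an expansion opens, and how it relates to the interim boundaries. Cover the case where the final criterion has become unreachable but no boundary is crossed.
- Say which boundary governs the first 15 patients at 100 units/m².
- Report the probability of meeting the criterion beside Tables 9 and 13. For at most 4/15 after the Table 8 looks, ignoring futility, it is 0.835, 0.515, 0.414, 0.217 and 0.059 at DLT rates of 0.20, 0.30, 0.33, 0.40 and 0.50.

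Which rule is right is for the sponsor to decide. The cost is a few sentences and a re-run of the operating characteristics. If the Section 4.0 limit is kept, the stated chance of declaring a dose safe will look less favourable at DLT rates of about 30% and above.
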